## Better BP Supplement

### Questionnaire Administration

1. **State Anxiety Index** (Prior to unattended and attended blood pressure measurements at visits 1 and 2 [based on randomization order]; during night of ABPM and HBPM)
2. **Trait Anxiety Index** (At visit 4 – optional to administer electronically)
3. **Expectations of Outcomes** (At visit 4 - optional to administer electronically)

### Examples of Questionnaire Administration

If participant is randomized to Unattended→Attended and ABPM → HBPM, please administer the questionnaires in the following order:

Visit 1	Visit 2	Visit 3	Visit 4
After office BP randomization, the state anxiety inventory will be administered unattended in concordance with the first clinic BP measurement.	After office BP randomization, the state anxiety inventory will be administered attended in concordance with the first clinic BP measurement.		After participants complete the device satisfaction questionnaire, the trait anxiety questionnaire and expectations of outcomes survey will be completed.
	After ABPM or home randomization, the state anxiety inventory will be completed at bedtime on the night of ABPM	After ABPM or home randomization, the state anxiety inventory will be completed at bedtime on the night of HBPM	

Unattended = give the participant the questionnaire and leave the room for 5 minutes

Attended = give the participant the questionnaire and remain in the room while they complete it

If participant is randomized to Attended→Unattended and HbPM → ABPM, please administer the questionnaires in the following order:

[figure not shown]
Visit 1	Visit 2	Visit 3	Visit 4
After office BP randomization, the state anxiety inventory will be administered attended in concordance with the first clinic BP measurement.	After office BP randomization, the state anxiety inventory will be administered unattended in concordance with the first clinic BP measurement.		After participants complete the device satisfaction questionnaire, the trait anxiety questionnaire and expectations of outcomes survey will be completed.
	After ABPM or home randomization, the state anxiety inventory will be completed at bedtime on the night of HbPM	After ABPM or home randomization, the state anxiety inventory will be completed at bedtime on the night of ABPM	

Unattended = give the participant the questionnaire and leave the room for 5 minutes

Attended = give the participant the questionnaire and remain in the room while they complete it

[figure not shown]
## Checking Statistics in REDCap

1. On the REDCap database home screen, in the applications panel to the left-hand side, select 'Data Exports, Reports, and Stats'.

The screenshot shows the REDCap interface for the 'Better BP Study' project. The left sidebar contains a list of applications, with 'Data Exports, Reports, and Stats' highlighted by a red arrow. The main content area displays the 'Data Exports, Reports, and Stats' module, which includes a brief description of its features and a table for managing reports. The table has two rows: 'All data (all records and fields)' and 'Selected instruments (all records)'. The 'Selected instruments' row has a 'Make custom selections' button, which is also highlighted by a red arrow.

2. Click on 'Selected Instruments – Make custom selections'.

The screenshot shows the 'Data Exports, Reports, and Stats' module with the 'Selected instruments' row selected. The 'Make custom selections' button in this row is highlighted by a red arrow. The rest of the interface is identical to the previous screenshot, showing the module's description and the 'All data' row.

### 3. Select 'Sociodemographic and Medical History' and click 'Stats & Charts'.

This module allows you to easily view reports of your data, inspect plots and descriptive statistics of your data, as well as export your data to Microsoft Excel, SAS, Stata, R, or SPSS for analysis (if you have such privileges). If you wish to export your \*entire\* data set or view it as a report, then Report A is the best and quickest way. However, if you want to view or export data from only specific instruments (or events) on the fly, then Report B is the best choice. You may also create your own custom reports below (if you have such privileges) in which you can filter the report to specific fields, records, or events using a vast array of filtering tools to make sure you get the exact data you want. Once you have created a report, you may view it as a webpage, export it out of REDCap in a specified format (Excel, SAS, Stata, SPSS, R), or view the plots and descriptive statistics for that report.

My Reports & Exports			
	Report name	View/Export Options	Management Options
A	All data (all records and fields)	View Report Export Data Stats & Charts	
		Select one or more instruments below for all records.	
B	Selected instruments (all records)	
Instruments
 
 -- All instruments --  Phonescript  Stopbang  Sociodemographic And Medical History      Pittsburgh Sleep Quality Index (PSQI) 
 View Report Export Data Stats & Charts   
- OR -
 + Create report based on the selections above	
		+ Create New Report	

4. You should now see statistics and plots for every question in this survey. If you would like to export the data, please select 'Export Data' in the top right hand corner.

Number of results returned: **26** View Report Export Data Print Page

Total number of records queried: 26

**Selected instruments (all records)**

**DISPLAY OPTIONS**

Optional: Select a record to overlay onto the plots below -- select record -- ▾

**Viewing options:** Show plots & stats Show plots only Show stats only

---

**1. What is your age?** (socio\_age) [Refresh Plot](#)

Total Count (N)	Missing	Unique	Min	Max	Mean	StDev	Sum	Percentile						
								0.05	0.10	0.25	0.50 Median	0.75	0.90	0.95
12	14 (53.8%)	11	24.00	78.00	51.08	15.61	613.00	26.75	30.10	42.25	50.50	62.00	64.70	70.85

Lowest values: 24, 29, 40, 43, 48  
 Highest values: 61, 62, 62, 65, 78

A scatter plot showing the distribution of age data. The x-axis ranges from 10 to 90 with major grid lines every 10 units. The y-axis represents the frequency of each age value. Most data points are blue, representing individual respondents. A single red dot is placed at the age value of 50.50, which is the median of the dataset.

Download image

## Calculating Better BP Results

### **Codebook Location (For REDCap data):**

O:\BetterBP\Data Dictionary

### **File Locations:**

```
libname data 'O:\BetterBP\Database Back-Up\November 2019';
libname echo 'O:\BetterBP\Echo Data';
libname labs 'O:\BetterBP\Lab Data';
```

### **Items to be calculated:**

1. Left ventricular mass index
2. Left ventricular ejection fraction
3. Average attended systolic blood pressure
4. Average attended diastolic blood pressure
5. Average attended heart rate
6. Average unattended systolic blood pressure
7. Average unattended diastolic blood pressure
8. Average unattended heart rate
9. Estimated glomerular filtration rate
10. Microalbumin-to-creatinine ratio

### **NOTES:**

- For the lab data, please use the 'month\_year\_clean' SAS datasets for analyses.
- I have noted the correct variables to use for the echo equations on the next page.
- Provided sample code for EGFR

### Echo Equations

**Left ventricular mass index (g/m^2) = Left ventricular mass (g)/ Body surface area (m^2)**

**Left ventricular mass (g) = 0.8 x 1.04 x [(A+B+C)-C] + 0.6**

A = Average of SWTd#1, SWTd#2, and SWTd#3 **[Variable: ivsd1...ivsd3]**

B = Average of PWTd#1, PWTd#2, and PWTd#3 **[Variable: pwt1...pwt3]**

C = Average of LVEDd#1, LVEDd#2, and LVEDd#3 **[Variable: lvidd1...lvidd3]**

**Body surface are (m^2) = 0.007184 x [height (cm)]0.725 x [weight (kg)]0.425**

**Left ventricular ejection fraction (%) = 100 x (D-E)/D**

D= Average of LVEDV#1, LVEDV#2, and LVEDV#3 **[Variable: lvedv1...lvedv3]**

E= Average of LVESV#1, LVESV#2, and LVESV#3 **[Variable: lvesv1...lvesv3]**

**[name]'s Example Code for Calculating EGFR (CKD-Epi Equation)**

```
**** Calculate estimated glomerular filtration rate;

if black=1 and male=0 and lbxscr<=0.7 then eGFR =166*((lbxscr/0.7)**(-0.329))*(0.993** (ridgeyr));

if black=1 and male=0 and lbxscr>0.7 then eGFR =166*((lbxscr/0.7)**(-1.209))*(0.993** (ridgeyr));

if black=1 and male=1 and lbxscr<=0.9 then eGFR =163*((lbxscr/0.9)**(-0.411))*(0.993** (ridgeyr));

if black=1 and male=1 and lbxscr>0.9 then eGFR =163*((lbxscr/0.9)**(-1.209))*(0.993** (ridgeyr));

if black=0 and male=0 and lbxscr<=0.7 then eGFR =144*((lbxscr/0.7)**(-0.329))*(0.993** (ridgeyr));

if black=0 and male=0 and lbxscr>0.7 then eGFR =144*((lbxscr/0.7)**(-1.209))*(0.993** (ridgeyr));

if black=0 and male=1 and lbxscr<=0.9 then eGFR =141*((lbxscr/0.9)**(-0.411))*(0.993** (ridgeyr));

if black=0 and male=1 and lbxscr>0.9 then eGFR=141*((lbxscr/0.9)**(-1.209))*(0.993** (ridgeyr));
```

## Telephone Screening Form

Confirm that you are speaking with the potential participant that has contacted us or who has filled out a contact card.

Introduction: We're enrolling 660 adults to take part in a research study about how to measure blood pressure. If you enroll, you will be asked to visit the UAB Hypertension Research Clinic four times for this study. We will try to schedule these visits on consecutive days but there may be a need to schedule these visits a few days apart. During the course of the study, you will have your blood pressure measured twelve times over your first two visits in the Hypertension Clinic, you will wear an automated blood pressure monitor that measures your blood pressure every 30 minutes for 24 hours, and you will wear a new blood pressure monitor that you put on before going to bed and it measures your blood pressure three times at night while you are asleep. Afterwards, you will answer some questions about your experience while wearing each of the monitors. At your last visit, we will ask you to provide a blood and urine sample and complete an echocardiogram. Does this sound like something you might be interested in doing? *If no—thank them for their time. If yes, see text for screen.*

Screen: Now I'd like to ask you a few questions to make sure you're eligible to participate. Go to question 1.

1. Are you willing to complete four or more study visits over the course of 2 weeks at UAB?

*If yes, go to question 2. If no, see text for not eligible.*

2. Do you have reliable transportation to and from UAB Hypertension Research Clinic located on 19th Street?

*If yes, go to question 3. If no, see text for not eligible.*

3. How old are you?

*If ≥ 19 years, go to question 4. If < 19 years, see text for not eligible.*

4. What is your sex?\*

*If female and age < 60 years, go to question 3. Otherwise, go to question 5.*

*\*The protocol specifies recruitment of 330 women and 330 men. Once the recruitment cap in each group is met, we will no longer accept participants in that group.*

5. Are you currently pregnant?

*If no, go to question 6. If yes, see text for not eligible.*

6. Which of the following race/ethnicities would you consider yourself?

*Non-Hispanic white*

*Non-Hispanic black*

*Non-Hispanic Asian*

*Hispanic*

*Other*

7. Are you currently taking medication for high blood pressure or hypertension?

*If no, go to question 8. If yes, see text for not eligible.*

8. Have you ever been told by a physician that you have sleep apnea?

*If yes, see text for not eligible. If no, administer STOP-BANG questionnaire.*

STOP		
Do you SNORE loudly (louder than talking or loud enough to be heard through closed doors)?	Yes	No
Do you often feel TIREd, fatigued, or sleepy during daytime?	Yes	No
Has anyone OBSERVED you stop breathing during your sleep?	Yes	No
Do you have or are you being treated for high blood PRESSURE?	Yes	No
BANG		
BMI more than 35kg/m^2?	Yes	No
AGE over 50 years old?	Yes	No
NECK circumference > 16 inches (40cm)?	Yes	No
GENDER: Male?	Yes	No
Total Score		

**High risk of OSA: Yes 5 - 8**

**Intermediate risk of OSA: Yes 3 - 4**

**Low risk of OSA: Yes 0 - 2**

\*If STOP-BANG score (minus neck circumference and BMI) is greater than 3, then see text for ineligible.

\*If STOP-BANG score (minus neck circumference and BMI) 3 or less, then see text for eligible.

9. Have you ever been told by a physician that you have heart disease?

*If no, go to question 9. If yes, see text for not eligible.*

10. Have you ever been told by a physician that you have had a heart attack?

*If no, go to question 10. If yes, see text for not eligible.*

11. Have you ever been told by a physician that you have had a stroke?

*If no, go to question 11. If yes, see text for not eligible.*

12. Have you ever been told by a physician that you have congestive heart failure?

*If no, go to question 12. If yes, see text for not eligible.*

13. Have you ever been told by a physician that you have an arrhythmia (e.g. atrial fibrillation and/or ventricular tachycardia)?

*If no, go to question 13. If yes, see text for not eligible.*

14. Have you ever had heart surgery?

*If no, go to question 14.*

*If yes, please ask them for the reason for the surgery.*

*If for revascularization or coronary artery bypass surgery, see text for ineligible.*

*If for other reasons (e.g. congenital heart defect), please go to question 14.*

15. Have you completed ABPM over 24 hours in the past year?

*If no, go to question 15. If yes, see text for not eligible.*

16. Do you work overnight shift (e.g. – 11pm to 7am)?

*If no, go to question 17. If yes, see text for not eligible.*

17. Do you have a permanent address?

*If yes, see text for not eligible.*

**Not eligible:** Sorry, it looks like you are not eligible to participate at this time. Thank you for taking the time to learn more about our study. I hope you have a nice day.

**Eligible:** Great! It looks like you are eligible to participate in the study. If I can collect your name and contact information, I will send you a consent form with more details.

Full Name \_\_\_\_\_

Email Address \_\_\_\_\_

Mailing Address \_\_\_\_\_

Phone Number \_\_\_\_\_

Thank you. Due to the current ongoing pandemic, we now have the option for you to complete your study documents electronically. Would you prefer to complete your study documents in-person or electronically?

Electronically

In-Person

If participant would like to complete forms **electronically**: We would like to give you time to read over the consent form and answer any questions you may have over a conference call. Can we schedule you for a conference call this week?

If participant would like to complete forms **in-person**: We would like to give you time to read over the consent form but we can find a convenient time for you to start the study. Can we schedule your first visit now?

Just to make you aware, prior to each of your in-person visits, we will ask you to complete COVID-19 screening questions and a temperature check. We also ask that you wear a mask to each of your visits. We will call and email you the day before your first visit as a reminder. Thank you for taking the time to learn about our study. I hope you have a nice day.

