### *Exclusion Criteria:*

- Taking antihypertensive medications
- Known to be pregnant
- History of sleep apnea
- History of cardiovascular disease, atrial fibrillation, and/or ventricular tachycardia
- High risk for sleep apnea, scoring 5 or greater on the STOP-BANG questionnaire
- Participants who work overnight shifts (11PM-7AM)
- Inability to wear the ABPM and/or HBPM devices and BP cuffs
- Completed ABPM in the past year
- No permanent residence

**Sites of Recruitment:** Columbia University Medical Center and University of Alabama at Birmingham

**Target sample size:** 315 participants with complete data.

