**Preparation for Visit 1 (Day of Appointment – before the participant arrives to the UAB Hypertension Research Clinic)**

- Just prior to the scheduled appointment, the research coordinator (RC) should do the following:
  - Confirm the participant is eligible:
    - Is their screening SBP between 110-159 mm Hg or DBP between 70-99 mm Hg and SBP < 160 mm Hg and DBP < 100 mm Hg?
    - Not currently taking antihypertensive medication?
    - No history of myocardial infarction, stroke, or arrhythmias?
    - Not currently pregnant?
    - Do they have an arm available for placement of a BP cuff?
    - Arm circumference <=52 cm?
    - Can rest their arm every 30 minutes for 24 hours to allow for a BP measurement?
    - Has not had an ABPM in the past year?
    - Does not work at night (or is completing ABPM on a non-work day with a one day wait following working the night shift)?
    - Is willing to return to the clinic after both the ABPM and HBPM periods to return the devices?
    - STOP-BANG score less than 4?
    - Do you have a permanent residence?
  - Enable REDCap Mobile with the questionnaires (Sociodemographic/Medical History and PSQI).
  - Initialize the WatchBP Office AFIB device.
  - Have the WatchBP Office AFIB device set up for the correct measurement intervals [5-minute initial rest period and 1-minute interval between readings].

**For participants who consent for the Better BP study at the beginning of study visit 1, please ask the participant if he/she needs to use the restroom prior to their height/weight/waist/neck measurements.**

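### The UAB telephone screening form's skip logic contradicts the protocol's exclusion criteria, and the check before Visit 1 only partly covers the gap

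*Combined protocol and SAP*

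**What the plan says.** The Exclusion Criteria in the manual list, among others, "History of cardiovascular disease, atrial fibrillation, and/or ventricular tachycardia" and "No permanent residence". They also exclude overnight-shift workers and anyone who has completed ABPM in the past year.

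The Telephone Screening Form is meant to apply these criteria. Its printed routing is as follows.

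- Question 4 (sex): "If female and age < 60 years, go to question 3. Otherwise, go to question 5". Question 3 asks age; question 5 asks about pregnancy.
- After question 8 the STOP-BANG items are scored without neck circumference and BMI. A score above 3 leads to the ineligible text; otherwise, "If STOP-BANG score (minus neck circumference and BMI) 3 or less, then see text for eligible".
- Question 9 (heart disease): "If no, go to question 9. If yes, see text for not eligible". Questions 10 to 15 follow the same pattern. They cover heart attack, stroke, heart failure, arrhythmia, heart surgery and, at question 15, "Have you completed ABPM over 24 hours in the past year".
- Question 16 (overnight work) sends a no to question 17.
- Question 17 asks "Do you have a permanent address" and sends a yes to the not-eligible text. It has no instruction for a no.

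The Summary section describes the call as settling preliminary eligibility only. The checklist under Preparation for Visit 1 has the coordinator confirm eligibility again. Its cardiovascular item reads "No history of myocardial infarction, stroke, or arrhythmias".

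**The concern.** The form states operational eligibility rules. If they are followed as printed, they give results that the Exclusion Criteria do not intend.

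The cardiovascular items matter most for Aim 3. Left ventricular mass index is one of its two end-organ markers, and prior heart failure or coronary disease can change it for reasons unrelated to the BP methods being compared. The Analysis Plan restricts Tables 9–11 to people with complete data and applies no exclusion for cardiovascular history. The night-work item bears on sleep BP: section D.4.1 of the research plan gives possibly different diurnal patterns as the reason for that exclusion.

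This point concerns the branching only, not the choice of STOP-BANG cut-off.

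**Working it through.** The plan states no figure to reproduce. The check is to trace every printed go-to or see-text instruction and compare the outcome with the Exclusion Criteria.

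**1. Routes to *Eligible*.** There is exactly one: the STOP-BANG branch at 3 or less. The other STOP-BANG branch ends in ineligible. Both exits therefore end the form after question 8, leaving 17 − 8 = 9 questions (9 to 17) that no printed route reaches.

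**2. Pointers that do not advance.** In questions 9 to 15 (seven questions) the acceptable answer points to the question's own number. Question 4 sends a woman under 60 to question 3, which returns her to question 4. Everyone else, men included, goes to the pregnancy question.

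**3. Two ways staff might use the form.**

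- *Stop at the STOP-BANG branch.* Callers with a score of 3 or less are passed on without the cardiovascular, prior-ABPM and night-work questions. Question 17 is never asked, so it rejects nobody.
- *Ask every question in order.* Questions 9 to 16 do screen. Question 17 then sends a yes to not eligible and a no nowhere, so nobody ends at *Eligible*. The Exclusion Criteria point the other way, because they exclude people without a residence.

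**4. What the check before Visit 1 recovers.**

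| Telephone item | Preparation for Visit 1 |
|---|---|
| Q9 heart disease | not named in general |
| Q10 heart attack | rechecked |
| Q11 stroke | rechecked |
| Q12 heart failure | not named |
| Q13 arrhythmia | rechecked |
| Q14 heart surgery, revascularisation | not named |
| Q15 ABPM in past year | rechecked |
| Q16 overnight work | rechecked, but a night worker is accepted on a non-work day after a one-day wait; the Exclusion Criteria give no such exception |
| Q17 permanent residence | rechecked, in the direction of the Exclusion Criteria |

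Five of the nine are rechecked, one is rechecked more loosely and three are not named. The other intake forms do not fill the three gaps. The medical history questionnaire (item 10) lists only hypertension, cholesterol, diabetes, and asthma or hay fever. The screening checklist, the Visit 1 checklist and the Visit 1 data form carry no cardiovascular history item.

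**5. Does the reported sample fit literal use?** Table 1 of the Analysis Plan gives 603 participants, 382 of them women, with a median age of 34.

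- Men: 603 − 382 = 221.
- Participants aged 34 or younger: about 603 / 2 ≈ 302.
- Women aged 34 or younger: at least about 302 − 221 = 81, even if every man were that young.

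The question 4 loop would have trapped all of these women. The printed pointers were therefore not followed literally for everyone, or many participants were screened in some other way.

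**The case against.** The strongest reply is that these are clerical slips in a preliminary script.

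- The *Eligible* text only collects contact details and leads to a consent form. A reader might infer that the form itself enrols excluded people. The documents do not support that, because eligibility is confirmed again before Visit 1. This stands.
- A reader might also infer that the form both admits excluded callers and turns away eligible ones. Those harms belong to the two incompatible uses in step 3 of the working. It would likewise be wrong to say that question 17 admits only people without an address: as printed, it admits nobody. This stands.
- The pointers in questions 9 to 15 look like stale numbering, and the sample in Table 1 shows that staff did not use the form literally for everyone. This stands, but it leaves the rule that staff actually used undocumented.
- Section D.4 of the research plan describes extracting medical history from health records before contact, which could catch cardiovascular disease. This stands only in part, since the manual's Recruitment Procedures rely on flyers and contact cards and mention no record extraction.
- The form is written for the UAB clinic, no Columbia form is in the documents, and the branching of the REDCap phone script is not shown. This stands: an error in REDCap or at Columbia cannot be assumed.
- Aim 3 compares BP measures within the same people, so a few participants with altered ventricular mass would not necessarily bias the comparison. Results are already tabulated, so correcting the form cannot change this sample. Both parts stand and limit the severity.

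What survives is the contradiction in the printed text, the three cardiovascular items with no second check, and the conflict on night work. Callers wrongly rejected at question 17 would also never reach the Visit 1 check.

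**Conclusion.** The point holds as a minor inconsistency among three places that should agree: the Telephone Screening Form, the Exclusion Criteria and the Preparation for Visit 1 checklist. Neither way of using the printed form gives a correct screen. The Visit 1 check gives partial protection. Heart failure, other heart disease and revascularisation are left unnamed, and the night-work item is looser than the Exclusion Criteria.

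It may be tempting to conclude that ineligible people entered the study and distorted the ventricular mass results. The documents show neither. They do not say how staff used the form, how REDCap branches, or whether any participant had a disqualifying history. The minimum age of 18 in Table 1, against a criterion of 19, might be read as proof of leaky screening. It could be a recording error, and it says nothing about cardiovascular history.

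The conclusion rests on the form being current as printed, and on no cardiovascular screen existing in pages that are not available.

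**What to change.** On the telephone form:

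- Change the STOP-BANG branch at 3 or less so that it goes to question 9, and place the only *Eligible* exit after question 17.
- Point each acceptable answer in questions 9 to 15 to the next question.
- At question 4, send women under 60 to question 5 and everyone else to question 6.
- Reverse question 17 so that no leads to not eligible and yes leads to eligible.

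Reconcile the cardiovascular and night-work items under Preparation for Visit 1 with the Exclusion Criteria. The investigators should state which night-work wording applies. Check whether the REDCap phone script carries the same routing, and correct it only if it does.

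For people already enrolled, query the REDCap phone-script records for blank or disqualifying answers to questions 9 to 17. If any participant is confirmed ineligible, rerun Tables 9–11 without them as a sensitivity analysis and report the number removed.

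The cost is an edit to one form and one checklist, a look at one REDCap instrument, and one data query. No new data collection is needed.
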